3.1.1 Definition of dose limiting toxicity

The dose limiting toxicity (DLT) and maximum tolerated dose (MTD) are defined using the National Cancer Institute (NCI) Common Terminology Criteria for Adverse Events (CTCAE) Version 4.02.

During the dose escalation phase, DLTs identified in Cycle 1 of combination treatment will inform the decisions to dose escalate through the increasing dose levels. DLTs will be defined throughout the treatment period during dose escalation and in the expansion cohort and will be considered in determining the RP2D. The criteria by which DLTs will be assessed against during Cycle 1 for dose escalation decisions are as follows:

A DLT is defined as an adverse event considered highly probable or probably related to vandetanib or selumetinib, that occurs during the first cycle of combination period:

- Death
- Neutropenia Grade 4 for ≥ 5 days duration (absolute neutrophil count (ANC) $<0.5 \times 10^9/L$) *

- Febrile neutropenia (fever of unknown origin without clinically or microbiologically documented infection) with Grade 3 or 4 neutropenia (absolute neutrophil count [ANC] $<1.0 \times 10^9/L$ and fever $\geq 38.5^{\circ}\text{C}$);
- Infection (documented clinically or microbiologically) with Grade 3 or 4 neutropenia (ANC $<1.0 \times 10^9/L$)
- Thrombocytopenia Grade 4: a) for ≥ 5 days *See footnote, or b) associated with active bleeding, or c) requiring platelet transfusion.
- Grade 3 or 4 toxicity to organs other than the bone marrow including Grade 3 and Grade 4 biochemical AEs.
- Grade 4 diarrhoea
- Any drug related toxicity that causes a treatment interruption for > 2 weeks (14 successive days). If a patient is deemed fit to restart treatment on Day 15 then this is not a DLT.
- QTc prolongation >500 msec
- Grade 4 hypertension.
- Persistent hypertension (defined as blood pressure $>160/100$ mmHg) sustained for >1 week despite optimal therapy.

EXCLUDING:

- Grade 3 nausea
- Grade 3 or 4 vomiting in patients (who have not received optimal treatment with anti-emetics)
- Grade 3 skin toxicity (and patients are receiving supportive measures to manage toxicity)
- Grade 3 diarrhoea in patients (who have not received optimal treatment with anti diarrhoeals)
- Alopecia (any grade)

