5.4 Dose modifications

5.4.1 Dose interruptions

In the event of drug related toxicity, drug administration must be withheld (except for skin, fatigue, nausea, myalgia or arthralgia, unless these specific toxicities do not respond to supportive measures) until Grade 1 or below or until the patient meets the eligibility criteria parameters.

- On observation of a Grade 2 cardiac toxicity (any causality), both vandetanib and selumetinib should be stopped until resolution.
- On observation of G3 diarrhoea, if this does not resolve within 48 hours, both vandetanib and selumetinib should be stopped until resolution (i.e. until Grade 0 or 1 or until the patient meets the eligibility criteria parameters).
- On observation of non-specific respiratory signs and symptoms, where infectious, neoplastic, and other causes are unlikely or have been excluded and a diagnosis of interstitial lung disease (ILD) is likely or confirmed, both IMPs should be interrupted.

Patients must meet eligibility criteria parameters prior to each cycle and following a treatment interruption if the intention is to re-treat.

The maximum unscheduled dose interruption period is two weeks. Patients failing to recover to NCI CTCAE Grade 1 or less after two weeks will be withdrawn from the study.

There are overlapping toxicities associated with both vandetanib and selumetinib. Therefore it may not be clear which agent is responsible for any observed toxicity. If this is the case then administration of both drugs must be stopped at the same time until resolution to the above criteria.

Vandetanib administration should not be interrupted if possible; the aim is to maintain vandetanib to reduce the requirement to repeat the 'loading' phase of vandetanib administration. Therefore on observation of a Grade 2 drug related toxicity, selumetinib alone can be stopped (vandetanib can continue as a single agent administration). The patient should be closely monitored (whilst on vandetanib alone) to ensure the toxicity resolves to Grade 1 or less within 24 hours. If toxicity continues at same grade or increases within 24 hours then vandetanib should also be stopped.

To note: selumetinib should not be given as a single agent.

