16.5 MANAGEMENT OF SKIN TOXICITY

Dermatological toxicity is anticipated for both vandetanib and selumetinib therefore the following guidance is recommended for patients on study and also guidance once study treatment has been discontinued. It is strongly recommended that all patients follow a program of sun protective measures while receiving study therapy and for 3-4 weeks after discontinuing study therapy. The aim is to reduce the risk of development of skin rash, minimize the severity of skin rash, and to minimize the requirement for dose reduction of study therapy. If a patient develops a skin rash, the following actions are recommended for the management of this reaction:

- A variety of agents can be used to manage skin rashes. These include mild to moderate strength steroid creams, either topical or systemic antibiotics, topical or systemic antihistamines, and occasionally retinoid creams. Patients with severe skin rashes, e.g., Stevens-Johnson Syndrome, toxic epidermal necrolysis, erythema multiforme, and toxic skin eruptions, should be treated with systemic glucocorticoids and should not continue treatment, even at a lower dose.
- The rash should be graded/assessed by a physician as soon as possible according to the NCI CTCAE (version 4.02) cutaneous toxicity criteria and documented accordingly
- If the rash is CTCAE Grade 1, consider starting with mild to moderate topical steroids (e.g., betamethasone), topical antibiotics such as clindamycin gel, systemic antibiotics or no treatment if the patient is asymptomatic.
- Please note: Use of topical steroid cream with higher potency may be considered early in patients with moderate rash on the face. Topical or systemic antihistamines, and occasionally retinoid creams can also be considered.
- If a rash of CTCAE Grade 2 or higher is detected, immediate symptomatic treatment should be provided e.g. topical steroid or pimecrolimus cream and consider adding an oral tetracycline or a similar agent.
- If a rash of CTCAE Grade 3 or higher is detected, study treatment must be withheld until recovery to Grade 1 or below (See Section 5.4). The addition of topical steroids is recommended.

Pruritus of any grade may be treated with an antihistamine, such as diphenhydramine or hydroxyzine hydrochloride.

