Secondary infection may complicate or worsen skin toxicity. To reduce the likelihood of nasal infection, intranasal mupirocin may be considered. Infected rash may be treated with a short course of an oral tetracycline, such as doxycycline. Sun exposure should be avoided in patients receiving doxycycline or other tetracycline antibiotics.

CONFIDENTIAL

If there is a clinical diagnosis of impetigo, or an infection with *Staphylococcus aureus* is confirmed, topical mupirocin might be used. Infected lesions suspected to be treatment-resistant should be cultured. If there is no improvement after two weeks of treatment, therapy for the rash should be considered ineffective and discontinued and study treatment should not re start.

Xerosis can be treated with classical emollients.

If severe cutaneous toxicity recurs at reduced dose of vandetanib and selumetinib, the patient will permanently discontinue study treatment.

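### The Grade 3 skin exclusion from DLT depends only on supportive measures being given, so a Grade 3 rash that persists on them but recovers within 14 days off drug is formally a non-DLT

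*Protocol*

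**What the plan says.** Section 3.1.1 makes a Grade 3 or 4 non-marrow toxicity a DLT if it is probably or highly probably related and falls in the first combination cycle. An EXCLUDING list follows. The skin entry reads "Grade 3 skin toxicity (and patients are receiving supportive measures to manage toxicity". The diarrhoea entry reads "Grade 3 diarrhoea in patients (who have not received optimal treatment with anti diarrhoeals", and the vomiting entry has the same form. Among the positive criteria, raised blood pressure counts when "sustained for >1 week despite optimal therapy". A drug-related interruption of more than 14 successive days is also a DLT, with the rider "If a patient is deemed fit to restart treatment on Day 15 then this is not a DLT".

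The management rules are elsewhere. Appendix 16.5 says "If a rash of CTCAE Grade 2 or higher is detected, immediate symptomatic treatment should be provided" and "If a rash of CTCAE Grade 3 or higher is detected, study treatment must be withheld until recovery to Grade 1 or below". Section 5.4.1 has a general hold rule for drug-related toxicity, "except for skin, fatigue, nausea, myalgia or arthralgia, unless these specific toxicities do not respond to supportive measures". Section 5.4.2.1 says the drug held responsible should restart one dose level lower. Section 3.1.3 removes a patient from dose-escalation decisions for too few doses only when the reason is not toxicity. Section 3.1.2 sets the MTD one level below the dose at which two of up to six patients have a DLT.

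**The concern.** In the diarrhoea, vomiting and hypertension entries, failure on adequate treatment makes the event dose limiting. The skin entry does the reverse: the event is excluded because treatment is under way, and nothing asks whether the treatment works. Read literally, an untreated Grade 3 rash counts and one that fails treatment does not.

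The formal DLT count sets the MTD, which is part of a primary endpoint. Section 2.3.4 expects that the two drugs together may make rash more frequent or more intense. The count can therefore be blind to part of a toxicity that the protocol itself anticipates.

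**Working it through.** The protocol gives no figure on this point, so there is nothing to reproduce. The check is a rule trace followed by an illustration.

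**Does the condition filter anything?** Appendix 16.5 calls for symptomatic treatment at Grade 2 or higher. A Grade 3 rash managed under that guidance therefore meets the skin condition from the start, and only a departure from the guidance would make it a DLT through this entry.

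**Rule trace for one patient**

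1. A related Grade 3 rash appears in the first combination cycle and supportive measures are given (16.5).
2. The rash persists. Drug is held, on detection under 16.5 or for non-response under 5.4.1.
3. It recovers to Grade 1 or below within 14 days, so the interruption criterion is not met (3.1.1).
4. The responsible drug should restart one level lower (5.4.2.1). A dose reduction is also what 5.4.2 prescribes after a DLT.
5. Any missed doses were missed for toxicity, so the patient stays evaluable (3.1.3).
6. Result: one evaluable patient with no DLT.

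**Where the gap ends.** Grade 4 rash is not excluded and counts. For rash that does not recover, 5.4.1 withdraws the patient after two weeks, and 16.5 says "If there is no improvement after two weeks of treatment, therapy for the rash should be considered ineffective and discontinued", with no restart of study treatment. Such cases appear to meet the interruption criterion, which covers any drug-related toxicity. The text does not say whether the EXCLUDING list overrides it.

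**Illustration.** Let b be the rate of other DLTs and r the rate of the rash class at issue. Both are assumptions, taken as independent; the protocol gives neither. If the class counted, p = 1 − (1 − b)(1 − r). Escalating on 0 of 3, or on 1 of 3 followed by 0 of 3, has probability

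P = (1 − p)³ + 3p(1 − p)⁵.

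Example with b = 0.10 and r = 0.05: p = 1 − 0.90 × 0.95 = 0.145, and P = 0.855³ + 3 × 0.145 × 0.855⁵ = 0.625 + 0.199 = 0.824.

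| Other DLTs, b | As written, any r | Counted, r = 2% | r = 5% | r = 10% |
|---|---|---|---|---|
| 5% | 0.973 | 0.952 | 0.910 | 0.824 |
| 10% | 0.906 | 0.875 | 0.824 | 0.730 |
| 20% | 0.709 | 0.674 | 0.622 | 0.536 |

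With six patients treated and b = 10%, the chance of two or more DLTs is 0.114 as written. It becomes 0.151, 0.212 or 0.320 with the class counted at 2%, 5% or 10%.

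The as-written column does not change with r: the formal count does not respond to this rash at all. The size of the change depends entirely on the assumed rates.

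**The case against.** The strongest reply is that this is a deliberate tolerability choice. The same list excludes Grade 3 nausea and alopecia of any grade without condition, so it has no uniform rule that failure on treatment is a DLT. Skin toxicity was expected with both drugs and has its own management appendix. This stands as a reason to keep manageable Grade 3 rash outside the definition. It does not explain a condition that the management rules satisfy automatically.

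Second, 16.5 holds drug on detection of Grade 3 rash, so supportive care and the hold start together. A bare test of whether the rash responds could hardly be judged. This stands, and it is why the remedy needs a fixed clock.

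Third, a reader might infer that these rashes go unseen and that escalation proceeds regardless. The documents do not support that. Section 5.3 brings other drug-related adverse events into dose assignment, has all adverse events reviewed at escalation meetings, and says only that escalation can be considered when there is no DLT. Section 3.1.2 allows escalation to stop before two DLTs and bases the expansion dose on all relevant toxicity data. Section 9.1 has Grade 3 skin events reported as medically important SAEs. What remains is that their weight is discretionary and the formal count is uncorrected.

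Fourth, the probabilities use invented rates, follow a 3+3 sequence rather than the rolling-six design, and ignore the adverse-event review. All of this is correct; they show direction only.

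**Conclusion.** The point holds as a minor-to-moderate defect of wording in a rule that sets the MTD. The skin condition filters almost nothing and is the reverse of the vomiting and diarrhoea conditions. The affected class is related Grade 3 rash that persists on supportive care but recovers within 14 days of a hold, with the responsible drug then reduced. The trace assumes that the 16.5 management guidance is followed.

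Two stronger readings should be resisted. One is that the MTD will be set too high: the protocol gives no rash rate, and dose decisions do not rest on the DLT count alone. The other is that section 2.3.5 shows this kind of rash making a similar combination intolerable: it cites Grade 3 rash together with diarrhoea and does not say that the rash failed supportive care.

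**What to change.** Amend 3.1.1 prospectively with two sentences.

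1. Exclude Grade 3 skin toxicity only if it improves to Grade 2 or below within a fixed time of starting optimal supportive measures, whether or not drug is held. Seven days would match the one-week limit in the hypertension entry. The clock should be mandatory, because the simultaneous hold makes response a matter of opinion otherwise.
2. State that the interruption criterion of more than 14 days, including permanent stops for rash, applies to skin toxicity despite the EXCLUDING list.

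Manageable Grade 3 rash stays outside the definition. Events at completed dose levels should not be reclassified. No separate listing is needed: the adverse-event review in 3.2.1 and 5.3 and the dose-modification and adverse-event summaries in 13.1 and 13.2 largely cover it.

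The cost is a short amendment. The downside is that escalation may stop slightly earlier.

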3.1.2 Definition of maximum tolerated dose

The MTD will be determined as the dose level below that at which two of up to six patients at the same dose level experience DLT in the first cycle of treatment (as defined in Section 3.1.1).

The maximum administered dose (MAD) could also equal the MTD in the event that dose escalation is stopped before two DLTs are observed at a given dose level due to the expectation that higher dose levels would be too toxic to administer to patients. The recommended dose for the expansion cohort evaluation will be determined following discussion of all the relevant toxicity data between the Sponsor (to include review by the

Protocol Safety and Review Board) and the Study Team, including the Chief Investigator and participating investigators.

3.1.3 Patient evaluability

Dose escalation:

All patients who meet the eligibility criteria and receive at least one dose of the combination treatment (vandetanib and selumetinib) will be evaluable for safety assessment.

Patients who receive fewer than 21 of 28 daily doses of the combination treatment in Cycle 1 (for reasons other than toxicity) will not be evaluable for dose escalation decisions.

Expansion cohort:

All patients who meet the eligibility criteria and receive at least one dose of the combination treatment (vandetanib and selumetinib) will be evaluable for safety assessment.

All patients who meet the eligibility criteria receive at least one cycle* of vandetanib and selumetinib and have a baseline assessment of disease will be evaluable for response. To be assigned a status of complete response (CR) or partial response (PR), changes in tumour measurements must be confirmed by repeat measurements performed no less than four weeks after the response criteria are met. To be assigned a status of stable disease (SD), follow-up measurements must have met the SD criteria at least once and at least six weeks after the initial dose of the combination treatment is given.

*To be evaluable for response, a patient must receive a minimum 21/28 daily doses of the combination treatment in Cycle 1.

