7.1.2 Evaluations within four weeks (28 days)

The following must be performed/obtained **within the four weeks before** the patient receives the first dose.

- Written informed consent (as detailed in Section 7.1.1)
- Demographic details
- Medical history including prior diagnosis, prior treatment, concomitant diseases and concomitant treatment
- Radiological Disease Assessments every 2 cycles
 - To include thoracic CT in expansion cohort
 - Radiological measurements using the most appropriate imaging for each patient using computerised tomography (CT) scan or magnetic resonance imaging (MRI) –must be performed **within four weeks before** the patient receives the first dose
- Bone scan (optional as clinically indicated)
- Ophthalmological exam (including slit lamp, visual acuity, visual fields, colour vision, optical coherence tomography (OCT) and intraocular pressure)
 - Adverse events relating to visual function have been reported in all studies with selumetinib to include blurred vision (please see IB supplement for further details of visual function toxicity). Therefore eye exams have been built into the schedule of events to allow for continuous assessment throughout study treatment.

Note that all adverse events (AEs), including serious adverse events (SAEs), must be monitored and recorded in the eCRF from the time the patient consents to any protocol-specific procedure (see Section 9 for further details).

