9 ASSESSMENT OF SAFETY

9.1 Adverse event definitions

Adverse event

For screening failures, serious adverse events (SAEs) will be reported to the Pharmacovigilance (PV) Department, Centre for Drug Development CDD from the date of consent until the date the patient is confirmed as ineligible.

For eligible patients, SAE and adverse event (AE) collection and monitoring commences from the time the patient gives their written consent to participate in the trial and continues for 28 days after the last administration of vandetanib and selumetinib (investigational medicinal products [IMPs]).

An AE is any untoward, undesired or unplanned occurrence in a patient administered an IMP, a comparator product or an approved drug. An AE can be a sign, symptom, disease, and/or laboratory or physiological observation that may or may not be related to the IMP or comparator.

An AE includes but is not limited to those in the following list.

- A clinically significant worsening of a pre-existing condition. This includes conditions that may resolve completely and then become abnormal again.
- AEs occurring from an overdose of an IMP, whether accidental or intentional.
- AEs occurring from lack of efficacy of an IMP, for example, if the Investigator suspects that a drug batch is not efficacious or if the Investigator suspects that the IMP has contributed to disease progression.

Other reportable events that must be treated as SAEs are listed below.

- Pregnancy exposure to the IMP. Any pregnancy occurring in a patient or a patient's partner during treatment with an IMP or occurring within six months of the last IMP administration, must be reported to the Pharmacovigilance Department in the same timelines as an SAE. These should be reported even if the patient is withdrawn from the trial.
- Overdose with or without an AE.
- Inadvertent or accidental exposure to an IMP with or without an AE, including for example, spillage of the IMP that contaminates staff.
- Any AE that could be related to the protocol procedures, and which could modify the conduct of the trial.

Serious adverse events (SAEs)

An SAE is any AE, regardless of dose, causality or expectedness, that:

- results in death;
- is life-threatening;
- requires in-patient hospitalisation or prolongs existing in-patient hospitalisation (some hospitalisations are exempt from SAE reporting – see Section 9.2);
- results in persistent or significant incapacity or disability;

- is a congenital anomaly or birth defect;

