9.3 Recording of adverse events and serious adverse events in eCRFs

All AEs, including SAEs, must be recorded in the eCRF for eligible patients. All concomitant medications, including herbal medications and supplements must be recorded. Any therapy used to treat the event must be recorded. The eCRF will be reconciled with the safety database during and at the end of the trial. Therefore, the sites should ensure the data entered on the SAE report form and the data entered into the eCRF are consistent. The CDD Medical Advisor and the Investigator(s) will regularly review the safety data from both the safety and the clinical database.

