13 DATA ANALYSIS AND STATISTICAL CONSIDERATIONS

The final analysis will be conducted after one of the following conditions is met.

- The trial is terminated early (for example, due to toxicity).
- All patients have completed their 'off-study' visit (i.e. 28 days after the last dose of vandetanib and selumetinib) and have been followed up for survival for one year from the first dose of IMP (Cycle 1 Day 1).

A clinical data cut-off date will be established to allow for primary analysis clinical study report (CSR) reporting once all recruited patients have been followed up for survival for a minimum of one year after the date of first IMP administration (Cycle 1 Day 1). The primary analysis CSR will include data from all treated patient visits/assessments up to and including the clinical cut-off date.

Any patients who continue to receive the combination therapy in the absence of disease progression or unacceptable toxicity after the clinical cut-off date will be included in an addendum to the final CSR. Only long-term safety data will be included in an addendum to the CSR.

PFS rate at 12 weeks will also be analysed for expansion cohort patients, according to the RECIST criteria. Assuming that the PFS rate in vandetanib alone is 9%, to test the hypotheses that the combination will increase the PFS rate to 23% under identical conditions, recruiting a total of 30 patients with NSCLC in a single arm design will give 82% power and 10% 1-side significant level.

The survival rate of NSCLC patients will also be analysed at one year. In addition to reporting the proportion of patients alive at 12 months, a Kaplan Meier curve will be plotted with 95% CI together with median survival provided.

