13.1 Presentation of data

Data will be presented in a descriptive fashion. Variables will be analysed to determine whether the criteria for the trial conduct are met. This will include a description of patients who did not meet all the eligibility criteria, an assessment of protocol violations, IMP accountability and other data that impact on the general conduct of the trial.

Baseline characteristics will be summarised (number and frequency) for all enrolled patients. Patients who died or withdrew before treatment started or did not complete the required safety observations will be described and evaluated separately.

Treatment administration will be described for all cycles. Dose administration, dose modifications or delays and the duration of therapy will be described.

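### The safety set in Protocol Section 3.1.3 leaves out dosed patients later found ineligible and patients who received only vandetanib

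*Protocol*

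**What the plan says.** **Protocol Section 3.1.3** uses one sentence, repeated for each phase, to say who counts for safety. It names them as "All patients who meet the eligibility criteria and receive at least one dose of the combination treatment". There are two conditions: eligibility, and at least one dose of the two drugs together.

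**Section 13** is wider: "The primary analysis CSR will include data from all treated patient visits/assessments up to and including the clinical cut-off date".

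**Section 13.1** plans a description of patients who failed one or more eligibility criteria, so it expects that some will exist. It also says that patients who died or withdrew before starting treatment, or who "did not complete the required safety observations will be described and evaluated separately".

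**Section 13.2** tabulates AEs by dose level but names no analysis population. Section 3.1.3 is therefore the only place in the protocol that says who is evaluable for safety.

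**On AE recording**, Section 9.3 says "All AEs, including SAEs, must be recorded in the eCRF for eligible patients". Section 7.1.2 has no eligibility condition: AEs "must be monitored and recorded in the eCRF from the time the patient consents to any protocol-specific procedure".

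**The concern.** A safety population should depend on exposure. Here it depends on exposure to the combination and also on eligibility, which may be reassessed after dosing. The first primary endpoint (Section 3.1) is the causality and grade of each adverse event, so any dosed patient outside the set takes real treatment toxicity out of the rates that answer that objective.

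Two groups are at issue.

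- **Dosed, later found ineligible.** Many of the criteria in Section 4.1 are cardiac, renal, hepatic, electrolyte or ocular limits. It is plausible, though the protocol gives no figure, that patients outside them have more toxicity. If so, leaving them out biases AE rates downward.
- **Vandetanib only.** Every patient takes vandetanib alone for 14 days, starting with a loading phase that Section 5.1.1 calls novel. A patient who stops in that period never receives the combination and so is not evaluable for safety, even if the reason for stopping was toxicity.

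**Working it through.** No figure in the protocol tests this point, so the check is a comparison of passages followed by an illustration of size.

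**Step 1. Who is in the set under each passage?**

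| Patient | Section 3.1.3 safety set | Section 13 primary report |
|---|---|---|
| Eligible, at least one combination dose | in | in |
| Combination dosed, later found ineligible | out | in |
| Eligible, vandetanib only | out | in |

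Nothing in the protocol says which passage governs the AE tables. Data can appear in the report while the patient is outside the evaluable denominator, so Section 13 does not settle the matter.

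**Step 2. Can the excluded patients arise?**

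- Ineligible but dosed: Section 13.1 plans to describe them. Section 14.1 allows no waivers, and Section 4.2 requires eligibility to be determined before enrolment. That rules out approved exceptions but not errors found later. The number should be small.
- Vandetanib only: Section 5.4.2.1 requires permanent discontinuation for vandetanib-related toxicity of Grade 3 or above during the single-agent period. This route is written into the plan and is the more predictable of the two.

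**Step 3. Do the dose-escalation rules carry the same condition?**

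No. Section 3.1.3 treats evaluability for dose decisions in a separate sentence, based on receiving 21 of 28 daily combination doses, with an exception for toxicity and no eligibility condition. Sections 3.2.1 and 5.3 count patients with dose-limiting toxicities (DLTs) at a level and use all available data. Ineligibility is not among the replacement criteria in Section 5.7.

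**Step 4. Illustration of size.**

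Let N patients be treated, x of them with a given toxicity, and let k of those x be left out. The reported rate is (x − k)/(N − k). A true rate of 20% is an assumption, as is the premise that every patient left out had the event.

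| | k = 0 | k = 1 | k = 2 | k = 3 |
|---|---|---|---|---|
| N = 30 (expansion), x = 6 | 20.0% | 5/29 = 17.2% | 4/28 = 14.3% | 3/27 = 11.1% |
| N = 80 (50 + 30, both phases at the upper planned number), x = 16 | 20.0% | 15/79 = 19.0% | 14/78 = 17.9% | 13/77 = 16.9% |

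The direction depends on who is left out. Removing one patient without the event from 30 gives 6/29 = 20.7%, a slight increase. The downward bias needs the excluded patients to have more toxicity than the rest. That is built into the vandetanib-only route through Grade 3 or higher toxicity, and is only plausible for the ineligible.

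**The case against.** The strongest reply is that nothing is lost. Section 13 reports all treated patients, serious adverse events (SAEs) must be reported under Section 9.2 without regard to eligibility, and the no-waiver policy makes dosed but ineligible patients rare. A statistical analysis plan, not shown here, may define a conventional safety set. The point about rarity stands and limits the size. The rest does not remove the problem: the protocol itself fixes a safety-evaluable set, and that set disagrees with Section 13. The no-waiver policy also does nothing about the vandetanib-only group.

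Three stronger readings are tempting, and the document does not support them.

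- **AEs in ineligible dosed patients need not be recorded.** A reader might infer this from Section 9.3. But in Section 9.1 the word *eligible* is set against screening failures, whose SAEs are reported "from the date of consent until the date the patient is confirmed as ineligible", while "For eligible patients, SAE and adverse event (AE) collection and monitoring commences from the time the patient gives their written consent". Section 7.1.2 requires recording from consent, and Section 7.2 requires AE assessment at each visit. This is loose wording, not a rule that discards data.
- **Patients with incomplete safety observations are dropped.** Section 13.1 says they are evaluated apart, which is not removal. The clause on death covers deaths before treatment, and a patient who stops for toxicity still has the off-study visit and 28-day follow-up. What stays open is whether treated patients with incomplete observations also count in the main tables.
- **A DLT in a patient later found ineligible could be discarded, turning 2 of 6 into 1 of 5.** Step 3 shows that the dose-decision rules have no eligibility condition, so this does not follow.

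**Conclusion.** The point holds for the safety-evaluable set. As written, Section 3.1.3 excludes dosed patients later found ineligible and patients who received only vandetanib from the set for the first primary objective, in conflict with Section 13. The effect is probably small: under the stated assumptions, about 3 percentage points in the expansion cohort (20.0% to 17.2%) or 1 point over 80 patients (20.0% to 19.0%) for each patient with an event who is left out. This rests on an assumed 20% event rate and on the excluded patients having had the event; the protocol gives no count of either group. Loss of AE data at site and an effect on dose-escalation decisions are not shown. It should be corrected because the objective is primary and the correction is cheap.

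**What to change.** - **Section 3.1.3, both safety sentences:** define the safety set as all patients who receive at least one dose of either vandetanib or selumetinib, regardless of eligibility, and make vandetanib-only patients identifiable in the tables. Deleting the eligibility phrase alone would not be enough, because the combination-dose condition would still leave out the vandetanib-only group.
- **Section 13.1:** state that treated patients with incomplete safety observations stay in the main safety tables and are also described separately.
- **Section 9.3:** keep recording from consent, and make clear that eligible patients means all enrolled patients, including any found ineligible after dosing, in line with Section 7.1.2. Tying this sentence to receipt of study drug should be avoided, since it would drop consented, eligible patients who have not yet been dosed.

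**Cost:** three wording changes, with no new data or patients. AE rates may look slightly less favourable, and the set will mix in some patients exposed to vandetanib only, which is why they need to be identifiable.
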